be asked for the incidence of cardiovascular events, such as any diagnosis of stroke, myocardial infarction or rupture of a abdominal aortic aneurysm.

- For the participants of the sub-study, the following procedures will be performed:
 - a) carotid and femoral artery ultrasound, b) heart ultrasound, and c) a blood sample of 10 ml (peripheral blood) will be collected for PBMC stimulation for cytokine production (see section "Sub-study procedures")

Visit 4 This visit is conducted 135 ± 5 days from the date of visit 1. This visit may be done by phone call or through the internet. During this visit, the vaccinated subject is asked to provide answers to a specific questionnaire involving the incidence of respiratory tract infection (Appendix VI). All patients will be asked for the incidence of cardiovascular events, such as any diagnosis of stroke, myocardial infarction or rupture of a abdominal aortic aneurysm.

Visit 5 This visit is conducted 180 ± 5 days from the date of visit 1. This visit may be done by phone call or through the internet. During this visit, the vaccinated subject is asked to provide answers to a specific questionnaire involving the incidence of respiratory tract infection (Appendix VI). All patients will be asked for the occurrence of cardiovascular events, such as any diagnosis of stroke, myocardial infarction or rupture of a abdominal aortic aneurysm. For the participants of the sub-study, the following procedures will be performed: a) carotid and femoral artery ultrasound, b) heart ultrasound, and c) a blood sample of 10 ml (peripheral blood) will be collected for PBMC stimulation for cytokine production (see section "Sub-study procedures")

It is explicitly stated that the investigators will encourage vaccinated population to refer to them in case of the incidence of any infection-related symptom.

PROCEDURES OF THE SUB-STUDY

Vaccinated people should abstain from food, alcohol and caffeine, smoking, and vasodilators for 12 hours before performing angiographic imaging studies. The exams to be taken are as follows:

- Arterial stiffness in the aorta from the speed of the pulse wave: It will be evaluated using a special non-invasive device (Complior, Artech Medical, France) in a non-bloody way on the carotid arteries and femoral arteries.

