- Positive respiratory questionnaire endpoint (as defined above) on visit 4
- Positive respiratory questionnaire endpoint (as defined above) on visit 5
- Prevalence of IgG/IgM against SARS-CoV-2 among the total of screened participants
- Itemized analysis of each of the components of the respiratory questionnaire on each study visit
- The incidence of new cardiovascular events on each study visit
- Differences in repeated measurements of vascular parameters (arterial hardness, central arterial pressures, reflected waves, endothelial function and carotid medial sheath thickness) in visit 3 between the two sub-study groups (placebo or BCG)
- Differences in repeated measurements of vascular parameters (arterial hardness, central arterial pressures, reflected waves, endothelial function and thickness of medial carotid sheath) and cardiac ultrasound at visit 5 between the two sub-study groups (placebo or BCG)
- Changes in the release of cytokines from blood mononuclear cells at visit 3 between the two sub-study groups (placebo or BCG)

STUDY POWER CALCULATION

The study is powered for the primary endpoint. The results of the interim analysis of the ACTIVATE study reveal 20.4% incidence of total respiratory infections

after three months from vaccination in the placebo group and 12.2% in the BCG group. To demonstrate this difference with 90% power at the 5% level of significance, 437 people need to be vaccinated per group. To adjust for losses to follow-up, we target to enroll 450 people per group.

To estimate the power of the sub-study, it is anticipated that there will be a difference greater or equal to 2% in endothelial-dependent vasodilation between the two interventions in visit 5. A total sample of 68 patients (with equally 34 individuals in each study group placebo or BCG) will highlight a difference with a power of 80% at the 10% level of significance. In order to adjust for possible losses of 10%, it is estimated that 75 patients should be admitted to the sub-study.

STATISTICAL ANALYSIS

Comparisons between the two groups will be done by the Fisher exact test. Any value of p below 0.05 will be considered as significant.

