The differences in the repeated measurements of the vascular parameters (arterial hardness, central arterial pressures, reflected waves, endothelial function and thickness of the inner-middle carotid sheath) will be estimated using randomly mixed models with two types: random effects (random intercept and random slope) and variance-covariance matrix. Vascular parameters will be used as dependent variables, after checking the normal distribution of their residuals with histograms and Q-Q plots graphs. In case of irregular distribution, appropriate transformations will be used (based on the neural index or using inverse ranking normalization).

INTERIM ANALYSIS

The Sponsor will appoint an independent committee to analyze the study and report the results of the primary endpoint once the last enrolled subject will reach visit 3. The study investigators will be informed on the results of the interim analysis but they will remain blind to the allocated arm of vaccination which will allow the study to end after the last visit of the last subject.

ADVERSE EVENTS

Adverse events (AEs) and Serious Adverse Events (SAEs) will be collected from baseline until the last patient's evaluation. Investigators should monitor subjects for adverse events and are responsible for recording ALL adverse events and serious adverse events occurring to a patient during the trial. Infection will not be reported as an SAE since this is the study primary endpoint.

An adverse event is any undesirable medical occurrence in a subject administered a pharmaceutical product and which does not necessarily have a causal relationship with this treatment. The time relationship is defined from the moment the AE occurs during therapeutic treatment until 30 days or 5 half-lives after treatment discontinuation. The adverse event may be a sign, a symptom, or an abnormal laboratory finding.

Serious adverse events (SAEs) must be reported to within 24 hours. If an adverse event meets any of the following criteria, it is considered SAE:

- **Death**
- **Life-threatening situation** The subject was at risk of death at the time of the adverse event/experience. It does not refer to the hypothetical risk of death if the AE were more severe or were to progress.
- **Inpatient hospitalization** or prolongation of existing hospitalization.

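### The only stated test that reaches the quantitative cytokine endpoint is Fisher's exact test, which would need an unstated cut-point and would lose power for that secondary endpoint

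*Protocol*

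**What the plan says.** The Secondary endpoints section of the protocol defines every secondary endpoint as a difference between the two vaccination groups. One of them is "Changes in the release of cytokines from blood mononuclear cells at visit 3 between the two sub-study groups (placebo or BCG".

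The Statistical Analysis section opens with a general rule, "Comparisons between the two groups will be done by the Fisher exact test", followed by "Any value of p below 0.05 will be considered as significant". Neither sentence is limited to a type of outcome. The next paragraph sets out one exception. "The differences in the repeated measurements of the vascular parameters", listed in brackets as arterial hardness, central pressures, reflected waves, endothelial function and carotid wall thickness, "will be estimated using randomly mixed models with two types: random effects (random intercept and random slope) and variance-covariance matrix". That paragraph also provides for residual checks and, where needed, a transformation. Neither cytokine release nor cardiac ultrasound is in the list.

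The Study visits section and Appendix IV schedule the cytokine assay for sub-study participants at visits 1, 3 and 5. At each of these visits "a blood sample of 10 ml (peripheral blood) will be collected for PBMC stimulation for cytokine production". The cytokine endpoint names visit 3 only. The vascular parameters have one endpoint at visit 3 and another at visit 5, and the latter also includes cardiac ultrasound.

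The sub-study is sized on a "difference greater or equal to 2% in endothelial-dependent vasodilation between the two interventions in visit 5": 34 per group, 80% power, 10% significance level. No power is claimed for cytokines.

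**The concern.** Fisher's exact test compares counts in categories, whereas cytokine release is measured on a scale. To follow the stated rule, the analyst must split the change into high and low at a point the protocol does not give. This has two consequences. Splitting discards information, which costs power in a comparison of about 34 per group. And a cut-point left open can be chosen after the data are seen.

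The Aim of the Study section gives the sub-study two purposes, endothelial function and mononuclear blood cells. Cytokine release is the only endpoint that serves the second.

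**Working it through.** **Which stated method applies.** The general sentence assigns group comparisons to Fisher's test. The exception covers a closed list without cytokines. No third method is stated, so Fisher's test is the only one that can reach this endpoint.

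**The plan's own figure.** No sample size is given for cytokines, and no SD for the vascular outcome, so 68 in total can be neither confirmed nor refuted. It can be solved backwards. With 34 per group, 80% power and two-sided 10%, the implied standardised effect is d = (1.645 + 0.842) × √(2/34) = 0.603, that is an SD of 2/0.603 = 3.32 points. If the 10% is one-sided, d is 0.515.

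**Assumptions.** The protocol gives no cytokine effect, SD, correlation or cut-point. I borrow d = 0.603 (in SDs of a single-visit value), take a baseline correlation r of 0.3, 0.5 or 0.7, assume a normal outcome on the scale analysed, and place the split midway between the group means.

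**Formulas, n = 34 per group.**
- Change score: standardised effect δ = d/√(2(1 − r)), giving 0.510, 0.603 and 0.779.
- Fisher's test on the split change: the proportions above the cut are Φ(δ/2) and 1 − Φ(δ/2), for example 0.62 and 0.38 at r = 0.5. Power is the sum of binomial probabilities over all tables with p below α.
- t-test on the change: noncentral t, 66 degrees of freedom, noncentrality δ√(34/2).
- Regression adjusted for visit 1: the same, with δ = d/√(1 − r²), giving 0.632, 0.696 and 0.844.

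**Power (%), two-sided.**

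| α | r | Fisher, split change | t-test, change | Adjusted regression | Fisher to adjusted, points |
|---|---|---|---|---|---|
| 5% | 0.3 | 28.4 | 54.4 | 72.9 | 44.5 |
| 5% | 0.5 | 39.3 | 68.8 | 80.8 | 41.5 |
| 5% | 0.7 | 61.5 | 88.6 | 92.9 | 31.4 |
| 10% | 0.3 | 43.9 | 66.8 | 82.5 | 38.6 |
| 10% | 0.5 | 55.9 | 79.3 | 88.4 | 32.5 |
| 10% | 0.7 | 76.4 | 93.7 | 96.4 | 20.0 |

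A simulation with 6,000 trials per correlation, an effect of 0.6 SD, a median split and the 5% level gave 29, 40 and 63% for Fisher's test and 72, 80 and 92% for adjusted regression, in agreement with the table.

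**Where the loss comes from.** At 5% and r = 0.5, splitting costs 68.8 − 39.3 = 29.5 points. A further 80.8 − 68.8 = 12.0 points separate the change score from baseline adjustment and have nothing to do with Fisher's test.

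**Sensitivity to the effect.** At 5% and r = 0.5, Fisher's test against adjusted regression gives 18% against 47% for d = 0.4, and 64% against 96% for d = 0.8.

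**The case against.** The best reply is that the Fisher sentence is generic and suits the binary primary endpoint and the binary questionnaire, antibody and cardiovascular-event outcomes. The next paragraph gives a continuous method for continuous outcomes, so the authors plainly do not treat Fisher's test as universal. On this view the cytokine method is simply unspecified and may be settled in a statistical analysis plan that is not at hand. Part of this stands: nowhere does the protocol say that cytokine release will be dichotomised, and the authors may never have meant it. But the sentence carries no limit and the exception is a closed list, so an analysis plan that used another method would depart from the protocol's text. That makes this a rule stated too broadly rather than a detail deferred.

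Three stronger readings are tempting, and the documents do not support them.
- *The visit 1 sample goes unused.* The endpoint is worded as a change, which implies the visit 1 value. What is missing is how it enters the comparison.
- *The sub-study loses about half its power.* It is sized on endothelial-dependent vasodilation, which has a mixed model that Fisher's test does not touch. Even for cytokines alone, the loss varies widely with assumed values.
- *Leaving out visit 5 costs power or is an error.* It does not weaken the visit 3 comparison unless both visits are pooled under a common effect, and a later sample may be kept for exploratory use. Making visit 5 a co-equal endpoint is a design preference.

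**Conclusion.** The point holds for the cytokine endpoint. The one stated rule that reaches it is a test that does not fit a quantitative outcome and needs an unstated cut-point. It had less power than the alternatives in every case computed. At the protocol's general 5% level the shortfall against baseline-adjusted regression is about 31 to 45 percentage points. At the 10% level used to size the sub-study it is about 20 to 39. These figures rest on an effect of 0.6 SD borrowed from the vascular calculation, 34 per group, a normal outcome, a central split and correlations of 0.3 to 0.7. None of the cytokine values is in the protocol, so they illustrate the loss and do not estimate it. This is a secondary endpoint: neither the primary comparison nor the sub-study's powered vascular endpoint is affected.

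**What to change.** Revise the Statistical Analysis section as follows.
- Restrict Fisher's exact test to binary outcomes.
- Compare cytokine release at visit 3 between groups with a linear model containing group and the visit 1 value, on a transformed scale if residual checks call for it, as the section already allows for the vascular parameters.
- Analyse the cardiac ultrasound measurements at visit 5 in the same way, adjusted for visit 1, since they too are outside the mixed-model list.
- State that the visit 5 cytokine sample, which no endpoint names, is analysed by the same model as a supportive result.

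The cost is wording only, because all samples and scans are already scheduled. The change should be made before any unblinded sub-study data are seen.

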Power of the study	
The study is powered for the primary endpoint. The results of the interim analysis of the ACTIVATE study reveal 20.4% incidence of total respiratory infections after three months from vaccination in the placebo group and 12.2% in the BCG group. To demonstrate this difference with 90% power at the 5% level of significance, 437 people need to be vaccinated per group. To adjust for losses to follow-up, we target to enroll 450 people per group.
 
To estimate the power of the sub-study, it is anticipated that there will be a difference greater or equal to 2% in endothelial-dependent vasodilation between the two interventions in visit 5. It is estimated that a total sample of 68 patients (equally 34 individuals in each study group-placebo and BCG) will highlight the difference with 80% power at a statistical significance level of 10%. In order to adjust for possible loss of 10%, it is estimated that 75 patients should be admitted to the sub-study.

Interim analysis	
Taking into consideration the situation of COVID-19 pandemic, an interim analysis is decided by the Sponsor when all patients reach visit 3

Study duration	
12 months

BACKGROUND

Infection by the novel SARS-CoV-2 virus (also known as COVID-19) has tremendous social impact. Most of Western societies are at major or part lockdown whatever brings unpredictable financial and societal consequences. The urgent need for the reversal of this situation can only be met through the generation of an immune defence shield to protect the society from COVID-19. Many efforts for the development of a vaccine are under way without any specific outcome so far.

The stimulation of trained immune responses seems the only alternative to bridge the gap from the turn-on of the society until the entrance of a specific vaccine in the market. Trained immunity stands for the non-specific raise of defence shield for severe infections coming once tissue macrophages recognize a universal pathogen¹. The concept was successfully tested in healthy volunteers that were vaccinated with placebo or BCG (Bacillus Calmette Guérin) vaccine. These volunteers were injected 14 days later a tri-valent influenza A vaccine. Volunteers previously vaccinated by BCG developed significantly greater titres against hemagglutinin A of the influenza A virus whereas their circulating monocytes were more potent for the production of interferon-gamma².

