Participants will be randomized at 1:1 ratio by a separate list per study site into two treatment groups. The list of randomization will be generated by a biostatistician and the randomization will be in a sealed envelope. The envelope will be delivered to the attending physicians after randomization. The two groups of treatment will be as follows:

- Placebo group: these participants will receive one intradermal injection of 0.1ml of sodium chloride 0.9%

- BCG group: these participants will receive one intradermal injection of 0.1ml of BCG (Bacillus Calmette Guérin Moscow strain 361- I, Serum Institute for India)

Patient screening and enrolment (APPENDIX IV)

In order for screening to proceed, the study will be advertised in the study site of the Hellenic Institute for the Study of Sepsis (www.sepsis.gr) and in the sites of other medical societies. The text to be used for the study advertisement is provided in APPENDIX V. People who will collaborate for the patient information will be GCP certified by the Sponsor.

Screening may start only after written informed consent is provided. Once written informed consent is provided, screening follows the following order:

- The patient is screened against the exclusion criteria. If the patient does not meet any exclusion criteria, screening proceeds to the next step.
- The patient is screened for inclusion criteria 1 to 4. If he does not meet all of them, it is a screening failure and screening stops. If he meets all of them, screening proceeds to the next step.
- The PPD Skin Test (inclusion criterion 5) is performed with an intradermal tuberculin injection into an forearm according to the manufacturer's instructions. The patient is asked to return in 48 hours to measure the skin hardness. If the diameter of the skin hardness is greater or equal to 10mm, it is considered as failure and screening process ends. If the diameter of the skin hardness is less than 10mm, screening process proceeds to the next step. This step can be omitted for patients who have undergone tuberculosis skin testing or a positive indirect detection test for *Mycobacterium tuberculosis* by determination of interferon- γ (IFN γ) after excitation of the last CD4- /CD8- cells for special peptides (IGRA) within the past five (5) years. In this case, any skin reaction with a fraction of less than 10 millimeters or a negative IGRA test allows the patient to enter the study.

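### Investigators are to be told the visit 3 result while some visit 4 and 5 data are still pending, which puts those secondary endpoints at risk of expectation bias and serves no decision stated in the plan

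*Protocol*

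**What the plan says.** In the Interim Analysis section, the task of an independent committee is to "analyze the study and report the results of the primary endpoint once the last enrolled subject will reach visit 3". On who then learns the outcome, the section says: "The study investigators will be informed on the results of the interim analysis but they will remain blind to the allocated arm of vaccination". Follow-up carries on regardless until every participant has had the final visit. The synopsis gives the reason as the pandemic situation and says that "an interim analysis is decided by the Sponsor when all patients reach visit 3". Neither place attaches a stopping, adaptation or crossover decision to the result. Neither says whether the arms are labelled or masked in what investigators receive, or whether participants are told.

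Under Study visits, visit 4 is at day 135 and visit 5 at day 180, each ± 5 days, and either may be held by phone or internet. Both collect the Appendix VI questionnaire and cardiovascular events. Sub-study participants also have vascular and cardiac ultrasound and blood sampling at visit 5. The Secondary endpoints section lists, as comparisons between the groups, the questionnaire endpoint at visit 4 and at visit 5, cardiovascular events at each visit, and the visit 5 vascular and cardiac measurements. The sub-study is powered on endothelial-dependent vasodilation at visit 5.

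**The concern.** The people told the result are those running a trial whose stated aim is a double-blind comparison, and follow-up is not finished. The primary endpoint is defined as a comparison of the two groups, so its results would naturally include the direction and size of the difference.

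The pending data have limited protection. Appendix IV schedules antibody testing at screening and visit 3 only, so the visit 4 and 5 endpoints have no serology. Apart from a known molecular diagnosis, the questionnaire rests on recalled symptoms, emergency attendance and antibiotic use. Investigators also encourage participants to contact them about infection symptoms between visits. An investigator who knows the direction of effect and suspects an arm could question or record differently by arm. What is at stake is the evidence on whether any protection lasts beyond three months, and the sub-study's visit 5 measurements.

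**Working it through.** The protocol gives no figure for the share of data outstanding at release, so there is none to reproduce.

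**1. Share of visits outstanding**

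Inputs: visits at days 90, 135 and 180 (Study visits); release once the last participant reaches day 90 (Interim Analysis); study duration 12 months (synopsis). Enrolment length E is not stated. Assumptions: uniform enrolment, immediate release, visit windows ignored.

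- Visit 4 is outstanding for those enrolled in the last 135 − 90 = 45 days: share = min(1, 45/E).
- Visit 5 is outstanding for those enrolled in the last 180 − 90 = 90 days: share = min(1, 90/E).

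If 12 months covers enrolment plus follow-up, E = 365 − 180 = 185 days (180 if 12 months is taken as 360 days).

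| E (days) | Visit 4 outstanding | Visit 5 outstanding |
|---|---|---|
| 60 | 75% | 100% |
| 90 | 50% | 100% |
| 120 | 37.5% | 75% |
| 180 | 25% | 50% |
| 185 | 24% | 49% |
| 240 | 19% | 37.5% |
| 300 | 15% | 30% |

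The last participant always has both visits ahead. A lag of L days between the last visit 3 and release lowers the shares to (45 − L)/E and (90 − L)/E. With L = 45 and E = 185, no visit 4 and 45/185 = 24% of visit 5 would remain.

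**2. What bias would require (illustration only)**

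Assume no true effect and a 20.4% rate in both arms with 437 per group. Both figures are borrowed from the power section; 20.4% is a three-month rate, whereas each questionnaire covers 45 days. Let f be the share outstanding, g the net share of correct guesses of arm (correct minus wrong), and r the relative shift in reporting, upwards for a guessed placebo and downwards for a guessed BCG.

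- Placebo rate = 0.204 × (1 + f·g·r); BCG rate = 0.204 × (1 − f·g·r).
- Risk ratio = (1 − f·g·r)/(1 + f·g·r).
- Type I error: two-sided 5% test of two proportions, normal approximation.

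| f | g | r | Risk ratio | Type I error |
|---|---|---|---|---|
| any | 0 | any | 1.000 | 5.0% |
| 0.24 | 25% | 10% | 0.988 | 5.1% |
| 0.24 | 50% | 25% | 0.942 | 7.3% |
| 0.49 | 25% | 10% | 0.976 | 5.4% |
| 0.49 | 50% | 25% | 0.885 | 15.0% |
| 1.00 | 25% | 10% | 0.951 | 6.6% |
| 1.00 | 50% | 25% | 0.778 | 46% |

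For example, f·g·r = 0.49 × 0.50 × 0.25 = 0.06125, so the rates are 21.65% and 19.15%, and the risk ratio is 0.93875/1.06125 = 0.885.

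The first row matters most: with no guessing above chance there is no differential bias, however much is outstanding. The protocol gives no values for g or r.

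**3. Primary endpoint**

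It uses visits 2 and 3 and the visit 3 antibodies. All of these are collected before the release.

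**The case against.** A reader might infer that the release by itself biases visits 4 and 5. The documents do not support this. The sentence that informs investigators also keeps them blind to allocation, and only investigators are said to be informed, although the answers come from participants. Differential bias needs an arm to be known or guessed. Nor does the text say that a labelled comparison is released. That is the natural reading, but masked labels are possible.

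A reader might also cite the statement that "The envelope will be delivered to the attending physicians after randomization" as proof that blinding has failed. If that step does reveal allocation, it does so from day 0 and also affects visits 2 and 3, so it is a separate matter. The protocol does not say that those physicians conduct visits 4 and 5. It does mean that the promise of continued blindness should not carry the whole weight.

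Three further points stand:

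- Several pending items are reported diagnoses or events (stroke, myocardial infarction, a molecular test, antibiotic use) and are less open to expectation than cough.
- Investigators already hold expectations, because the protocol itself presents the earlier trial's favourable interim result. The release adds to these by an unknown amount.
- The pandemic is a fair reason for an early analysis.

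The last point justifies giving the result to the sponsor. It does not explain why investigators need it while the study runs to its last visit regardless. Masking the labels helps only in part: the size of the difference would still be disclosed, and its direction would be easy to presume from the protocol's background section.

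**Conclusion.** The point holds as a risk to secondary endpoints. The protocol fixes, as an explicit rule, a disclosure to investigators before follow-up ends, and states no decision that the disclosure serves. Exposed are the questionnaire and cardiovascular endpoints at visits 4 and 5, and possibly the sub-study's visit 5 ultrasound. The primary endpoint is complete and unaffected, and this single look at it needs no adjustment of the significance level.

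The central estimate of one quarter of visit 4 and one half of visit 5 data outstanding rests on uniform enrolment over about 180 to 185 days and immediate release. The assumed enrolment lengths of 60 to 300 days give the wide ranges shown. Visit 5 is wholly outstanding only if enrolment takes 90 days or less. The type I error figures show what guessing could do. They do not predict what it will do. Because the remedy costs little, it is worth making, but the trial's main conclusion does not depend on it.

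**What to change.** Change the Interim Analysis section, and align the synopsis, to state that:

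- the independent committee reports the visit 3 comparison only to a sponsor group separated from trial conduct;
- investigators and site staff receive no comparative result, labelled or masked, until the last visit 5 is complete and the data are locked;
- if the sponsor releases the result earlier because of the pandemic, each visit 4 and visit 5 record is flagged as collected before or after release, and a sensitivity analysis compares the arms on pre-release data only.

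The restricted analysis would be imperfect: it uses fewer data (about 76% of visit 4 and 51% of visit 5 under the 185-day assumption) and an earlier calendar period. It would still show whether a difference at visits 4 and 5 depends on data collected after release.

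Cost: wording and slightly more analysis work. Sample size and the sponsor's early access are unchanged. Investigators learn the result about 180 − 90 = 90 days later.
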